#### **8.10.5 Critical Procedures Based on Study Objectives: Timing of Procedure**

For this study, the blood sample for MK-8189 is the critical procedure.

At any postdose time point, the blood sample for MK-8189 needs to be collected as close to the exact time point as possible. All other procedures should be completed as close to the prescribed/scheduled time as possible. Study procedures can be performed prior or after the prescribed/scheduled time.

The order of priority can be changed during the study with joint agreement of the investigator and the Sponsor Clinical Director. Blood samples should be taken after vital sign and ECG assessments or there should be a 10-minute window between a blood draw and the start of a vital sign or ECG assessment.

Any nonscheduled procedures required for urgent evaluation of safety concerns take precedence over all routine scheduled procedures.

The following variance in procedure collection times will be permitted.

- PK collections may be obtained:
  - Predose within 1 hour prior to dosing
  - within +/- 20 minutes of all postdose theoretical timepoints.
- Predose standard safety evaluations:
  - Vital signs within 15 minutes from the theoretical timepoint
  - ECG within 2 hours prior to first dose
  - Laboratory safety tests and physical exam within 48 hours prior to first dose
- Postdose standard safety evaluations:
  - Vital signs and ECG within 20 minutes from the theoretical timepoint
  - Laboratory safety tests within 90 minutes prior to the theoretical timepoint
- Study intervention administration may be given within 30 minutes from the theoretical timepoint.

#### **8.10.6 Study Design/Dosing/Procedures Modifications Permitted Within Protocol Parameters**

This is a Phase 1 assessment of MK-8189 in humans, and the PK, PD, and safety profiles of the compound are still being elucidated. This protocol is written with some flexibility to accommodate the inherent dynamic nature of Phase 1 clinical studies. Modifications to the dose, dosing regimen, and/or clinical or laboratory procedures currently outlined may be required to achieve the scientific goals of the study objectives and/or to ensure appropriate safety monitoring of the study participants.

As such, some alterations from the currently outlined dose and/or dosing regimen may be permitted based on newly available data, but the maximum daily dose may not exceed those currently outlined in the protocol.

- Repeat of or decrease in the dose of the study intervention administered in any given panel
- Repeat of a Panel at the same dose regimen or more conservative dose regimen.
- Entire panels may be omitted
- Adjustment of the dosing interval (eg, divided doses [BID to QD, QD to BID, TID, or vice versa])

- Addition of PK pause
- Instructions to take study intervention with or without food or drink may also be modified based on newly available data
- Modification of the PK sample processing and shipping details based on newly available data
- A single dose may be skipped, and dosing may continue at the same dose level or adjusted downward.

The PK/PD sampling scheme currently outlined in the protocol may be modified during the study based on newly available PK or PD data (eg, to obtain data closer to the time of peak plasma concentrations). If indicated, these collected samples may also be assayed in an exploratory manner for metabolites and/or additional pharmacodynamic markers.

Up to additional 50 mL of blood may be drawn for safety, PK, and/or PD analyses. The total blood volume withdrawn from any single participant will not exceed the maximum allowable volume during his/her participation in the entire study (Appendix 8).

The timing of procedures for assessment of safety procedures (eg, vital signs, ECG, safety laboratory tests, etc.) may be modified during the study based on newly available data. Additional laboratory safety tests may be added to blood samples previously drawn to obtain additional safety information. These changes will not increase the number of study procedures for a given participant during his/her participation in the entire study.

It is understood that the current study may employ some or none of the alterations described above. Any alteration made to this protocol to meet the study objectives must be detailed by the Sponsor in a letter to the Study File and forwarded to the investigator for retention. The letter may be forwarded to the IRB/IEC at the discretion of the investigator.

## **9 STATISTICAL ANALYSIS PLAN**

### **9.1 Statistical Analysis Plan Summary**

This section contains a brief summary of the statistical analyses for this trial. Full detail is in the Statistical Analysis Plan (Section 9.2).

Safety: Summary statistics and plots will be generated for raw laboratory safety tests, 12-lead ECGs, and/or VS as well as for change from baseline, as deemed clinically appropriate. Depending on the safety parameter, the difference from baseline will either be computed on the original scale (raw change from baseline) or on the log scale and back-transformed for reporting (percent change from baseline). For vital signs, time-matched Day -1 readings will be used as baseline. For all other endpoints, baseline is defined as average of predose Day 1 or Day -1 readings.

For all panels, summary statistics and plots will be generated for BARS, AIMS and SAS, VAS, and BPRS as well as for change from baseline. Responses to the C-SSRS will be listed.

**Pharmacokinetics:**

Separately for each part and each PK parameter, individual values of AUC0-24hr, Cmax, and C24hr at each dose level will be natural log-transformed and evaluated with a linear mixed effects model containing a fixed effect for dose and a random effect for subject. For each PK parameter, GM and corresponding ninety-five percent Cis for each dose will be provided.

The comparison of elderly participants with schizophrenia to young adults with schizophrenia will be made using data from Part 2 and Part 1, and historical data from P007 (Panel B and D). Separately for each PK parameter individual values of AUC0-24hr, Cmax, and C24hr at each dose level (16 mg and 24 mg at steady state) will be natural log-transformed and evaluated with a linear mixed effects model containing fixed effects for dose, population (elderly, adult), and population by dose interaction and a random effect for subject. For each population, GMs and corresponding 95% CIs for each dose will be provided. Similarly, the comparison of healthy elderly participants (Panels F and G) to healthy young adults (Panel A in P007) will be made using the above described model.

**9.2 Responsibility for Analyses**

The statistical analysis of the data obtained from this study will be conducted by, or under the direct auspices of, the Early Clinical Development Statistics Department in collaboration with the Quantitative Pharmacology and Pharmacometrics Department and Translational Pharmacology Department of the Sponsor. If, after the study has begun, changes are made to the statistical analysis plan stated below, then these deviations to the plan will be listed, along with an explanation as to why they occurred, in the Clinical Study Report.

**9.3 Hypotheses/Estimation**

**Objectives**

**Primary**

**Part 1**

- To evaluate the safety and tolerability of MK-8189 oral, once-daily titration regimens in young adult participants with schizophrenia

**Part 2**

To evaluate the safety and tolerability of multiple once-daily oral doses of MK-8189 in elderly participants with schizophrenia and healthy elderly participants.

**Secondary**

**Part 1**

- To characterize MK-8189 pharmacokinetics following different titration regimens in young adult participants with schizophrenia

## Part 2

- To characterize the pharmacokinetics of MK-8189 following multiple once-daily oral doses in elderly participants with schizophrenia and in healthy participants.

### Exploratory

#### Part 1 and Part 2

- To investigate the relationship between CYP2C9 genetic polymorphs and the PK and PD of MK-8189. Genetic variation in CYP2C9 may be analyzed for association with any laboratory or clinical data collected in this study.
- To explore the relationship between genetic variation and response to the treatment administered, and mechanisms of disease. Variation across the human genome may be analyzed for association with clinical data collected in this study.

## Part 2

- To compare the pharmacokinetics of MK-8189 in elderly participants with schizophrenia to dose-matched young adult participants with schizophrenia

To compare the pharmacokinetics of MK-8189 in elderly healthy participants to dose-matched healthy young adult participants.

## **9.4 Analysis Endpoints**

Safety: Primary safety endpoints will include all types of adverse experiences, in addition to laboratory safety tests, 12-lead ECGs, and VS. For vital signs, time-matched Day -1 readings will be used as baseline. For all other endpoints, baseline is defined as the predose Day 1 or Day -1 readings, as appropriate.

For all panels, summary statistics will be generated for BARS, AIMS, SAS, VAS, and BPRS as well as for change from baseline. The difference from baseline will be computed on the original scale (raw change from baseline). Responses to the C-SSRS will be listed. The C-SSRS will be used to systematically and prospectively ascertain and document the occurrence of suicidal events (ie, ideation and behavior). Responses on the C-SSRS are classified according to 11 prespecified categories as described in the operations manual. The most severe treatment-emergent ideation and behavior event reported at a visit will be used for analysis and reporting. An event is considered treatment-emergent during the assessment phase if it newly emerged or is more severe compared to recent history (ie, protocol-defined recent history prior to entering the trial as stated in the Inclusion/Exclusion criteria for suicidal ideation/behavior, up to and including the randomization visit).

### Secondary Endpoints

Pharmacokinetics: MK-8189 PK variables (AUC0-24hr, Cmax, C24hr, Tmax, CL, Vd and t1/2) are of secondary interest in adult and elderly participants with schizophrenia and healthy participants

### Exploratory Endpoints

Comparison of young adults versus elderly: MK-8189 PK\_variables MK-8189 (AUC0-24hr, Cmax, C24hr, Tmax, CL, Vd, and apparent t1/2).

## **9.5 Analysis Populations**

The following populations are defined for the analysis and reporting of data. All participants will be reported, and their data analyzed, according to the treatment(s) they actually received.

*All Participants as Treated (ApasT):* The All Participants as Treated Population consists of all participants who received at least one dose of treatment. This population will be used for assessments of safety and tolerability.

*Per-Protocol (PP):* The Per-Protocol Population consists of the set of data generated by the subset of participants who comply with the protocol sufficiently to ensure that these data will be likely to exhibit the effects of treatment, according to the underlying scientific model. Compliance covers such considerations as exposure to treatment, availability of measurements and absence of important protocol deviations. Important protocol deviations will be identified to the extent possible prior to unblinding by individuals responsible for data collection/compliance, and its analysis and interpretation. Any participants or data values excluded from analysis will be identified, along with their reason for exclusion, in the CSR. At the end of the study, all participants who are compliant with the study procedure as aforementioned and have available data from at least one treatment (dose level) will be included in the Per-Protocol dataset. This population will be used for the PK analysis.

## **9.6 Statistical Methods**

### **Safety**

Summary statistics and plots will be generated for raw laboratory safety tests, 12-lead ECGs, and/or VS as well as for change from baseline, as deemed clinically appropriate. Depending on the safety parameter, the difference from baseline will either be computed on the original scale (raw change from baseline) or on the log scale and back-transformed for reporting (percent change from baseline). For vital signs, time-matched Day -1 readings will be used as baseline. For all other endpoints, baseline is defined as the predose Day 1 or Day -1 readings, as appropriate.

For both parts, summary statistics and plots will be generated for BARS, AIMS, SAS, VAS, and BPRS as well as for change from baseline. Responses to the C-SSRS will be listed.

## Pharmacokinetics

Separately for each part and each PK parameter, individual values of AUC0-24hr, Cmax, and C24hr at each dose level will be natural log-transformed and evaluated with a linear mixed effects model containing a fixed effect for dose and a random effect for subject. For each PK parameter, GM and corresponding 95% CI for each dose will be provided.

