In P005, for the primary endpoint of PANSS total score change from baseline at Week 4, although the MK-8189 group showed meaningful improvement in symptoms, the improvement missed statistical significance (difference [95% CI] in LS mean change was -4.7 [-9.8, 0.5];  $p=0.074$ ). Risperidone was superior to placebo with respect to this endpoint (difference [95% CI] in LS mean change was -7.3 [-14.0, -0.6];  $p=0.033$ ). There was no difference in magnitude of effect between MK-8189 and risperidone (difference [95% CI] in LS mean change was 2.6 [-4.0, 9.2];  $p=0.440$ ). For the exploratory endpoint of PANSS positive subscale score at Week 4, both MK-8189 and risperidone were superior to placebo. There was no significant difference in effect between MK-8189 and risperidone. Neither risperidone nor MK-8189 demonstrated significant improvement in the CGI-S.

Median Tmax of MK-8189 as monotherapy ranged from 10 to 20 hours with a t1/2 of approximately 8.4 hours (37.8% GCV).

Data suggest that the exposures at steady state for a given dose are generally lower in healthy participants compared to participants with schizophrenia administered MK-8189 as monotherapy.

In a DDI study (P006) the coadministration of extended release 240-mg diltiazem increased MK-8189 AUC and Cmax by approximately 2-fold and 1.3-fold, respectively, confirming that MK-8189 is a CYP3A substrate.

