## 3 HYPOTHESES, OBJECTIVES, AND ENDPOINTS

There are no hypotheses for this study.

In male or female participants with schizophrenia (young adults and elderly) and healthy elderly participants:

Objectives	Endpoints
Primary	
Part 1 

To evaluate the safety and tolerability of MK-8189 oral, once-daily titration regimens in young adult participants with schizophrenia

	Part 1 and Part 2 

Adverse experiences, laboratory safety tests, electrocardiograms and vital signs

Part 2 

To evaluate the safety and tolerability of multiple once-daily oral doses of MK-8189 in elderly participants with schizophrenia and healthy elderly participants

	

Objectives	Endpoints
Secondary	
Part 1 

To characterize MK-8189 pharmacokinetics following different titration regimens in young adult participants with schizophrenia

	Part 1 and Part 2 

AUC0-24hr, Cmax, C24hr, Tmax, CL, Vd and apparent t1/2

Part 2 

To characterize the pharmacokinetics of MK-8189 following multiple once-daily oral doses in elderly participants with schizophrenia and healthy elderly participants.

	
Tertiary/Exploratory	
Part 1 and Part 2 

To investigate the relationship between CYP2C9 genetic polymorphisms and the PK of MK-8189. Genetic variation in CYP2C9 may be analyzed for association with any laboratory or clinical data collected in this study.

To explore the relationship between genetic variation and response to the treatment administered, and mechanisms of disease. Variation across the human genome may be analyzed for association with clinical data collected in this study.

	Part 1 and Part 2 

Germline genetic variation in CYP2C9 and association to clinical data collected in this study

Germline genetic variation and association to clinical data collected in this study.

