If tolerability issues are due to elimination of dose titration, it will likely be evident within the first few days of dosing MK-8189. Thus, an initial assessment of tolerability will be made following 3 days of dosing in approximately 8 participants. If MK-8189 is generally well tolerated based on AEs, an additional 8 participants will be enrolled into Panel B receiving Titration Regimen 2. If Titration Regimen 2 is not generally well tolerated in Panel B (either after assessment of the initial cohort [n=8] or full cohort [n=16]), an additional 8 participants

will be enrolled in Panel A such that a total of 16 participants will receive Titration Regimen 1.

Panel C will enroll 16 participants with schizophrenia disorder and receive Titration Regimen 3. Participants will be randomized to active or placebo. Participants randomized to MK-8189 will receive 8 mg on Day 1 (2 x 4-mg tablets), 16 mg on Day 2 (1 x 12-mg tablet and 1 x 4-mg tablet) and 24 mg (2 x 12-mg tablets) on Days 3 to 7. Participants randomized to placebo will receive the same number of tablets matching the MK-8189 tablet strength in the active group.

All participants will be confined to the unit from at least Day -6 until Day 9 assessments are complete.

## Part 2

The goal of Part 2 is to evaluate MK-8189 safety, tolerability and PK and titration regimens in elderly participants with schizophrenia disorder (Panels D and E) and healthy elderly participants (Panel F and G). Participants will be randomized to MK-8189 or placebo. Participants with schizophrenia will be washed off their current antipsychotic therapy. The washout may start with a down titration of the antipsychotic treatment during the screening phase per direction of the investigator. Participants should not receive antipsychotics for at least 5 days or 3 half-lives (whichever is longer) prior to Day -1. For longer half-life antipsychotics (e.g. aripiprazole and brexpiprazole), if deemed appropriate by the investigator, a participant may stop treatment (i.e. cessation of AAP) as an outpatient, but should be confined the clinical research unit within a week of stopping treatment and minimally beginning on Day -6. Healthy elderly participants (Panel F and G) will be domiciled by Day -1.

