## 4.2 Scientific Rationale for Study Design

### Part 1

In the current trial, a staged approach will be implemented to evaluate the need for titration. Alternate dose regimens will be evaluated based on tolerability as described in Section 4.1. While MK-8189 was generally well tolerated in both healthy participants and participants with schizophrenia (P003 and P007), the schizophrenia population was selected for evaluation in the current trial as preliminary PK data suggest that MK-8189 exposures may be greater in the patient population at doses greater than 12 mg. A matched placebo-control will be included to reduce bias with regards to the patient reporting and investigator assessment of AEs.

### Part 2

As schizophrenia is a life-long disease, it is likely the elderly will be an important segment of the MK-8189 treatment population. This study part is being conducted to evaluate the safety, tolerability and PK of MK-8189 in the elderly population. For Panel D and Panel F, the dose regimen selected has been tolerated in young adult participants with schizophrenia and will be the dose regimen in the Phase 2b study. For Panel E and Panel G, the titration regimen selected will be based on safety and tolerability results of Part 2, Panel D and Panel F, respectively and from Part 1 of the current protocol. In Panel E and Panel G, a small cohort will initially be dosed. If there are no tolerability concerns, the remainder of the cohort will proceed with dosing on the selected regimen. If there are tolerability concerns, the remainder of patients may be dosed with an alternative titration regimen as described in Section 4.1.

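### As written, the secondary Part 2 PK model pools elderly participants with schizophrenia and healthy elderly into one geometric mean and 95% CI per dose

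*Combined protocol and SAP*

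**What the plan says.** Section 9.6, Pharmacokinetics (repeated in Section 9.1), sets the unit of analysis: "Separately for each part and each PK parameter, individual values of AUC0-24hr, Cmax, and C24hr at each dose level". The values are log-transformed and analysed with "a linear mixed effects model containing a fixed effect for dose and a random effect for subject", and one GM and 95% CI are reported per dose. There is no population term, and no sentence divides this model by population.

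Part 2 enrols both groups: Panels D and E with schizophrenia, Panels F and G healthy. Section 3 states the Part 2 secondary PK objective as characterisation "following multiple once-daily oral doses in elderly participants with schizophrenia and healthy elderly participants". Section 9.3 repeats it with slightly different wording: "To characterize the pharmacokinetics of MK-8189 following multiple once-daily oral doses in elderly participants with schizophrenia and in healthy participants". Section 9.4 says the PK variables "are of secondary interest in adult and elderly participants with schizophrenia and healthy participants".

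Two other parts of Section 9.6 bear on the point:

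- **Comparison of Elderly Participants and Young Adults (exploratory).** This runs the schizophrenia and healthy comparisons separately. It gives population GMs with 95% CIs at 16 mg and 24 mg, not at 8 mg.
- **Descriptive Statistics.** This gives N, GM and geometric CV by part, panel and dose. The statistics are non-model-based and include no CI.

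**The concern.** A single GM per dose is a fair summary only if the two groups have similar exposure. The protocol gives reason to doubt that. Section 2.2.2 reports: "Data suggest that the exposures at steady state for a given dose are generally lower in healthy participants compared to participants with schizophrenia". Section 4.2 adds that "preliminary PK data suggest that MK-8189 exposures may be greater in the patient population at doses greater than 12 mg", a range that includes 16 mg and 24 mg. Neither statement gives a size or concerns the elderly specifically.

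The model also assumes one between-subject and one residual variance for everyone. The planning SDs in Table 4 (Section 9.9) differ by population: 0.38 against 0.60 for log AUC0-24hr, and 0.48 against 1.11 for log C24hr. The variance ratios are 0.60²/0.38² = 2.5 and 1.11²/0.48² = 5.3.

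If exposures do differ, the analysis attached to the secondary objective reports an enrolment-weighted value that describes neither group. It would stand in the study report beside different exploratory GMs for the same participants.

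A likely origin, which is inference only, is that Amendment 05 added Panels F and G. Before that, Part 2 held only participants with schizophrenia, so fitting by part was enough.

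**Working it through.** **Inputs.** Log between-subject SDs for AUC0-24hr are taken from Table 4: s1 = 0.38 (schizophrenia) and s2 = 0.60 (healthy). They come from P007 at 24 mg, not from elderly participants. Active numbers are from Table 2 (Section 6.3.1) with one regimen each in Panels E and G: n1 = 12 + 12 = 24 and n2 = 10 + 10 = 20, so N = 44. The healthy/patient ratio r is not in the documents. It is assumed, over the range 0.7 to 1.0.

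**Check on the inputs.** Table 4's log half-widths reproduce as t(0.95, n1+n2−2) × SD × √(1/n1 + 1/n2). For schizophrenia, 12 against 12: 1.717 × 0.38 × √(2/12) = 0.266. For healthy, 10 against 12: 1.725 × 0.60 × √(1/10 + 1/12) = 0.443. Both match the table.

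**Bias of the pooled GM.** Let d = −ln r. The pooled GM is exp(−d·n2/N) times the patient GM and exp(d·n1/N) times the healthy GM. At r = 0.8, d = 0.2231:

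- against patients: exp(−0.2231 × 20/44) = 0.904
- against healthy: exp(0.2231 × 24/44) = 1.129

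**Coverage of the pooled 95% CI.** The expected pooled variance is [(n1−1)s1² + (n2−1)s2² + (n1n2/N)(d² + s1²/n1 + s2²/n2)]/(N−1).

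- At r = 0.8 this is (3.321 + 6.840 + 0.805)/43 = 0.2550, so SD = 0.505.
- Half-width h = 2.017 × 0.505/√44 = 0.154.
- True SE of the pooled mean = √(24 × 0.1444 + 20 × 0.36)/44 = 0.0742.
- The biases on the log scale are 0.101 (patients) and 0.122 (healthy).
- Coverage is Φ((h − bias)/SE) − Φ((−h − bias)/SE), which gives 0.76 for patients and 0.67 for healthy.

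| Assumed r | Pooled GM below patients / above healthy | Coverage, patients / healthy |
|---|---|---|
| 1.0 | none | about 96% for both |
| 0.9 | 5% / 6% | 91% / 89% |
| 0.8 | 10% / 13% | 76% / 67% |
| 0.7 | 15% / 21% | about 48% / 32% |

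The bias hardly depends on enrolment, but coverage does. At r = 0.8, coverage is 82/75% with 18 + 15 active (Panels D and F stopped at their initial cohorts) and 67/61% with 30 + 27 (Panels E and G at their maxima).

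This treats one dose level at a time. A REML simulation of the mixed model over all three doses (600 runs, Regimen 1 in Panels E/G, assumed within-subject correlation 0.8) gave 24 mg coverage of 90/86% at r = 0.9 and 76/66% at r = 0.8.

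**Precision after a split, 24 mg.** For healthy elderly, n = 20: 2.093 × 0.60/√20 = 0.28 on the log scale. The pooled fit gives 0.15.

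**Precision after a split, 8 mg.** With Regimen 1 in Panels E/G, only Panels D and F receive 8 mg. Panels E and G still inform the 8 mg mean through the subject effect. Assume the Table 4 SDs hold at 8 mg and within-subject correlation is ρ. The variance of the 8 mg log mean is then s²[(1−R²)/a + R²/b], where R² = 2ρ²/(1+ρ), a is the number given 8 mg and b the number in the population.

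- Patients (a = 12, b = 24, 23 df) at ρ = 0.8: R² = 0.711 and the half-width is 2.069 × 0.38 × √(0.289/12 + 0.711/24) = 0.18.
- Healthy (a = 10, b = 20, 19 df) at ρ = 0.8: 2.093 × 0.60 × √(0.289/10 + 0.711/20) = 0.32.
- Over ρ = 0.5 to 0.9 the ranges are about 0.17 to 0.21 (patients) and 0.30 to 0.36 (healthy).

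**The case against.** The strongest reply is that the groups are already separated where it matters. The exploratory comparison gives population GMs and 95% CIs at 16 mg and 24 mg, the doses at which exposures might differ. The descriptive statistics give GM and geometric CV by panel, from which a t-based CI can be derived even at 8 mg. This stands, and it keeps the point small. A reader might infer that the plan never reports group-specific PK; that would be wrong. What remains is that the exploratory model also draws on young-adult and historical data, the descriptive statistics include no CI, and neither changes what the secondary model is written to produce.

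A reader might also infer that the objective demands separate inference for each group. It does not say so. Section 3 joins both groups in one bullet, whereas the exploratory comparisons have one bullet per population. The secondary text names both groups and no more.

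The size is open too. The exposure ratio is assumed, and at 1.0 nothing is lost. Table 4's healthy SDs come from P007 Panel A, which mixed Japanese and non-Japanese participants with 12 on active, so part of the SD contrast may reflect that mix.

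Finally, the sponsor may intend separate fits. That is plausible, but the text does not say it, and Section 9.2 requires changes to the plan to be listed and explained in the study report.

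**Conclusion.** The point holds, at minor severity. Read as written, the secondary Part 2 model pools Panels D/E with Panels F/G under one GM, one 95% CI per dose and common variances, against the protocol's own indications of different exposure and spread.

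At an assumed AUC ratio of 0.8 with 24 + 20 active, the pooled GM is 10% below patients and 13% above healthy elderly, with coverage of about 76% and 67%. At 0.9 coverage is 91% and 89%. At 1.0 there is no bias and coverage is about 96%. These figures rest on the assumed ratio and on SDs from non-elderly P007 participants at 24 mg.

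The harm is limited to the secondary model's own result and to the absence of a printed population-specific CI at 8 mg. A reader might infer that titration or panel decisions are at risk. The documents do not support that: Section 4.1 bases those decisions on safety and tolerability, and the study has no hypotheses.

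**What to change.** In Sections 9.1 and 9.6, extend the opening clause of the secondary PK paragraph to read: *separately for each part and, in Part 2, for each population (Panels D/E; Panels F/G)*. Report GM and 95% CI per dose within each population. Separate fits also give each population its own variances, and the split matches the one already used in the exploratory comparison.

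The change needs no new data and touches no dose or clinical rule. Its cost is a wider interval for healthy elderly: an AUC log half-width of about 0.28 instead of 0.15 at 24 mg with n = 20. At 8 mg it supplies the missing intervals, with AUC log half-widths of about 0.17 to 0.21 (patients) and 0.30 to 0.36 (healthy) under the assumptions above.
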